## **Outcomes**

### **Primary:**

Disease control rate (DCR). Defined by absence of radiological progression in conventional imaging examinations by RECIST 1.1 at 6 months after the end of treatment. For patients with functioning syndrome, beside radiological DCR, patients should have improved in at least 10% of the baseline score of quality-of-life (EORTC QLQ-GINET21) and stability or decrease in tumor markers.

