## **Methodology**

### **Study design**

This is a single-arm, unicentric, single-stage, phase 2 clinical study of therapeutic metaiodobenzylguanidine (MIBG) for patients with metastatic well-differentiated neuroendocrine tumors and radiological progression or intolerance after standard lines of treatment and with MIBG-I positive scan.

Eligible patients will receive MIBG-I in up to 4 doses of 7,400Mbq (200 mCi) each, with an interval of at least 60 days. The administration of the cycles will depend on the results of the haematological exams, therefore, each patient will be able to receive from 1 to 4 cycles; In the experience of A.C.Camargo Cancer Center, most patients receive between 3 and 4 cycles. MIBG-I is administered intravenously to an inpatient, being discharged when reaching limits of radiological exposure recommended by the National Nuclear Energy Commission (invariably, 24 hours). The dose of 200mCi

per application for up to 4 doses of MIBG-I used in this protocol is the same used in routine at the institution and is also used in other PPRT treatments. This dose is safe and practiced by the service for at least a decade.

Clinical and toxicity assessments will take place every 2 weeks with medical history, physical examination and general laboratory until resolution of toxicities (usually 30 days after treatment). Imaging exams (chest, abdomen and pelvis CT scans) and 5-HIAA dosage in 24-hour urine (functioning tumors) will be performed at the beginning of treatment, and every 3 months until progression or exit from the study. Symptom assessment will be conducted using quality of life questionnaires that will be administered before treatment and every 3 months until progression. Toxicities will be measured in all medical visits through CTCAE version 5.0. Consultations, laboratory and imaging tests are already part of the treatment routine of these patients. The extra routine interventions, that is, the study, are the MIBG-I scintigraphy exam, the treatment with MIBG-I and the quality-of-life assessments.

Clinical data will be prospectively collected in an electronic database (REDCap) and will include sex, age, primary tumor site, performance scale status, functionality, metastatic disease duration, metastasis sites, degree of liver impairment, comorbidities, previous treatments, scores of quality of life results and toxicity.

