MIBG-I is administered at a dose of 200mCi intravenously every 8 weeks for up to 4 cycles. Laboratory tests are performed every 15 days, with a focus on assessing myelotoxicity. Laboratory blood tests within the appropriate results (see “inclusion criteria”) allow the administration of the next cycle. In the case of any toxicity with a degree equal to or greater than 3 or intolerable and persistent grade 2 toxicity, the next course of treatment will not be administered until the toxicity is grade 1 or resolves. If the toxicity does not resolve or becomes grade 1 within 8 weeks, the next cycle is not administered, and treatment is stopped.

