### **Potential for cost-effectiveness**

Treatment with MIBG-I, in addition to being available at SUS for the treatment of patients with PggF, appears to offer significant disease control for patients with NET. If the study is positive, it can be cost-effective, as we estimate that 67% of patients will obtain disease control lasting at least 12 months, which will provide time free of toxic therapies, with a low level of evidence and costly to patients and paying sources. In addition, in the absence of a clinical study, these toxic and ineffective therapies are used sequentially, so that each patient will do, in the period of 12 months, at least two of them.

**Table 1.** Treatments used in midgut NET or refractory lung, respective toxicities, efficacy and levels of scientific evidence

Treatment	Disease control rate (%)	Time of disease control (months)	Common toxicities	Evidence level
Folfox/Capox	0-10%	4 – 6	Peripheric neuropathy, diarrhea, nausea, vomiting, thrombocytopenia, anaemia	Retrospective, heterogeneous population*
Capecitabine/ Temozolomide	0-10%	4 – 6	Nausea/Vomiting, diarrhea	Retrospective, phase 1/2 with heterogeneous population
Interferon alpha (3 to 6 million units/week)	20 – 30% (symptoms), 50% (radiological)	10	Psychiatric disorders, immunes, fatigue, myopathy, myelosuppression	Phase III for radiological control, retrospective studies for symptomatic control
Debulking hepatic surgery (R2)	50 – 90% (only symptoms)	19 – 45	Surgical risk compared to a hepatectomy	Retrospective, heterogeneous population
MIBG- 	63 – 80%	12 – 24	Myelosuppression	Retrospective, heterogeneous population

\* neuroendocrine tumors of different origin, efficacy measured with distinct criteria

**TABLE 2.** Complete procedural summary of the study after signing the informed consent form

Procedure	Screening *	Baseline evaluation	D1 **	S2 **	S4 **	...	S8 **	S12 **	S16 **	...	S24 **	Every 12 or 8 weeks
Eligibility assessment												
MIBG scan	X											
Demographics, medical history and previous treatment	X											
Therapeutic MIBG												
200mCi MIBG-  I IV administration			X				X		X		X	
Clinical safety assessment												
Physical exam		X	X	X	X	X	X	X	X	X	X	X
Vital signs, body weight and ECOG		X	X	X	X	X	X	X	X	X	X	X
Signs and symptoms assessment		X	X	X	X	X	X	X	X	X	X	X
Adverse Event Assessment		X		X	X	X	X	X	X	X	X	X

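### Primary DCR is timed from the end of a one-to-four-dose course, so required control from first dose runs from about 26 to 50 weeks, against a single 40% null labelled a 6-month rate

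*Combined protocol and SAP*

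**What the plan says.** Outcomes (Primary) sets the DCR as "Defined by absence of radiological progression in conventional imaging examinations by RECIST 1.1 at 6 months after the end of treatment". Patients with a functioning syndrome must also improve on GINET21 and have stable or falling markers.

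The length of treatment is not fixed. Study design says "The administration of the cycles will depend on the results of the haematological exams" and that "each patient will be able to receive from 1 to 4 cycles", adding that in the centre's experience most patients receive three or four. The section on high-dose treatment says that, after qualifying toxicity, "the next course of treatment will not be administered until the toxicity is grade 1 or resolves". It continues: "If the toxicity does not resolve or becomes grade 1 within 8 weeks, the next cycle is not administered, and treatment is stopped".

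Spacing is given in two ways. The high-dose section says the drug "is administered at a dose of 200mCi intravenously every 8 weeks for up to 4 cycles", and Table 2 marks its row "200mCi MIBG- 131 I IV administration" at D1, S8, S16 and S24. Study design and the Abstract give doses "with an interval of at least 60 days".

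The Statistical plan evaluates efficacy in everyone who receives at least one dose. It sizes the trial on H0 = 40% and H1 = 67%. The Abstract ties the 40% to 6 months in placebo arms, whereas the Statistical plan attaches it to 40 months. Progression-free survival (PFS), by contrast, runs from day 1 of cycle 1. Imaging is every 12 weeks until progression or withdrawal.

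**The concern.** The landmark moves with the end of treatment, and the end of treatment is itself affected by treatment. Two patients with the same time to progression, say week 40, can be classified differently: after one dose the patient is a success at week 26, and after four doses a failure at week 50. The pooled proportion then depends partly on how many cycles patients happened to receive, which the plan cannot fix in advance.

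A single-arm trial has only its benchmark for comparison. A placebo rate at 6 months describes control over 6 months from the start of observation. Most patients here would be judged over a considerably longer span from first dose. At stake is whether a positive or negative result in 22 patients reflects the drug or a mismatch between the endpoint's time span and that of the null.

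**Working it through.** **1. The plan's own figure.** Inputs from the Statistical plan: H0 = 0.40, H1 = 0.67, two-sided alpha 10% (z = 1.645), power 80% (z = 0.842), loss 10%.

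n = [(1.645·√(0.40·0.60) + 0.842·√(0.67·0.33)) / 0.27]² = 19.8, so 20. Then 20 × 1.1 = 22 (dividing by 0.9 instead gives 23). The stated 22 is reproduced, so this point concerns timing and not the sample-size arithmetic.

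**2. Required progression-free time from first dose.** With k doses, 8-week spacing (Table 2), 6 months taken as 26 weeks, and the end of treatment read as the last dose: h = 8(k − 1) + 26.

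| Doses | Week judged, 8-week spacing | Week judged, 60-day spacing |
|---|---|---|
| 1 | 26 | 26 |
| 2 | 34 | 34.6 |
| 3 | 42 | 43.1 |
| 4 | 50 | 51.7 |

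The four-dose requirement is 50/26 = 1.92 times the one-dose requirement. With a full 8-week hold, counted from the due date, before each of the three later doses, it would reach 3 × 16 + 26 = 74 weeks.

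**3. What this does to the rates.** Assumption: constant progression hazard, unrelated to number of doses. If rate p applies at week r, the rate at week h is p^(h/r).

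| Rate and anchor | 1 dose | 2 | 3 | 4 |
|---|---|---|---|---|
| 40% at week 26 | 40.0% | 30.2% | 22.8% | 17.2% |
| 67% at week 26 | 67.0% | 59.2% | 52.4% | 46.3% |
| 40% at week 50 | 62.1% | 53.6% | 46.3% | 40.0% |

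Relaxing the constant hazard to Weibull shapes 0.7 to 1.5 moves the four-dose figure to between 23.5% and 8.7% (from 40% at week 26) and between 53.1% and 34.4% (from 67%).

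**4. Pooled rates.** The documents give no cycle distribution beyond most patients receiving three or four. An illustrative mix is 3/3/8/8 patients with 1/2/3/4 doses, so 16 of 22 have three or four.

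- 40% at week 26: (3×0.400 + 3×0.302 + 8×0.228 + 8×0.172)/22 = 24%.
- 67% at week 26: (3×0.670 + 3×0.592 + 8×0.524 + 8×0.463)/22 = 53%.
- 40% at week 50: (3×0.621 + 3×0.536 + 8×0.463 + 8×0.400)/22 = 47%.

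**5. Effect on the conclusion.** No success cut-off is stated, so two are shown. At p = 0.40 with 22 patients, at least 13 successes has probability 5.5% and at least 14 has 2.1%. Only 14 keeps the upper tail within 5%. The mixed-dose probabilities sum independent patients, each with the rate for their own number of doses.

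| Case | Probability | Cut-off 13/22 | Cut-off 14/22 |
|---|---|---|---|
| 67% applies to every patient | success if drug works as planned | 85% | 72% |
| 67% at week 26, 3/3/8/8 mix | success if drug works as planned | 36% | 22% |
| 40% applies to every patient | false positive | 5.5% | 2.1% |
| 40% at week 50, 3/3/8/8 mix | false positive | 18% | 8.9% |
| 40% at week 26, 3/3/8/8 mix | false positive | below 0.1% | below 0.1% |

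**The case against.** Control lasting 6 months beyond a finite course is a coherent clinical question, and the Abstract, Objectives and Outcomes state it consistently. PFS from day 1 of cycle 1 is already a secondary endpoint with Kaplan-Meier reporting, so fixed-time rates could be read from a planned analysis. Both statements are right. They argue for keeping the present DCR as a durability measure. They do not give it a matching benchmark, because the 40% is compared with the moving landmark and not with a fixed-time rate.

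A reader might infer that success is easiest for those who tolerate MIBG worst. The documents do not support that in general. Unresolved toxicity that stops treatment shortens the required time, but toxicity that resolves delays the next dose and lengthens it. Patients who stop for progression fail at any landmark. A one-dose patient with about 1.9 times the hazard of a four-dose patient would lose the advantage, and the documents give no data on hazard by dose number. In functioning tumours the added GINET21 and marker conditions may also offset it.

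A reader might also infer a plain inflation of false positives, to as much as 28% at 13/22. That figure needs the 40% placed at week 50, a cut-off that the plan does not state, and a 6/5/5/6 mix. That mix gives only 11 of 22 patients three or four doses, against the protocol's expectation that most will receive that many. On the Abstract's 6-month reading, false positives are negligible and the loss is in power.

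Two further limits stand. The 74-week figure is an extreme, since the plan does not say when the 8-week hold begins. And the end of treatment is undefined: if it means the decision to stop after a hold, a one-dose patient is judged at about week 8 + 8 + 26 = 42. The gap to week 50 narrows, but the order is unchanged.

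**Conclusion.** The point holds as one of endpoint definition and benchmark match. The 26/34/42/50-week spread follows directly from the protocol's schedule, given 8-week spacing and the last dose as the end of treatment. That these patients are pooled against one null is also in the text.

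The size of the effect on the trial's conclusion is illustrative. It rests on a constant hazard unrelated to dose number, an assumed cycle mix and an assumed cut-off. Its direction depends on when the 40% applies. On the Abstract's 6-month reading, the more likely harm is discarding an active treatment. With the 40% placed at week 50, it is a raised false-positive risk. The Statistical plan's 40-month label settles neither. The change is worth making before analysis, with medium confidence in how much it matters.

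**What to change.** 1. Pre-specify the Kaplan-Meier progression-free rate from day 1 of cycle 1 at week 24 (the scan nearest the 6-month benchmark) and week 48 (near the four-dose landmark).
2. Make the comparison with the historical rate at one of these fixed times. State H0, H1 and the success cut-off for that time, and correct the conflict between the 6-month and 40-month labels on the 40%.
3. Define the end of treatment: the date of the last dose or the date of the decision to stop.
4. Keep DCR at 6 months after the end of treatment as a durability measure, and report it by number of doses received. Whether the fixed-time rate becomes the primary endpoint is for the sponsor to decide, since that changes the clinical question.
5. Reconcile the two statements of the dosing interval (8 weeks, and at least 60 days), because the landmark depends on it.

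Cost: protocol and SAP wording. No extra scans are needed, since imaging already runs every 12 weeks until progression. The real work is restating the planning rates for the chosen time. The Kaplan-Meier rate would also inherit the PFS rule that censors at the last MIBG date when new treatment starts without radiological progression, so that rule should be stated alongside it.

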## **Objectives**

### **Primary:**

- 1 - Control of radiological disease at 6 months after the end of treatment.
- 2- Control of clinical/biochemical (functional NET) at 6 months after the end of treatment.

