### **Secondary:**

1- Disease control rate (DCR). Defined by absence of radiological progression in conventional imaging examinations by RECIST 1.1 at 3 months after the end of treatment. For patients with functioning syndrome, beside radiological DCR, patients should have improved in at least 10% of the baseline score of quality-of-life (EORTC QLQ-GINET21) and stability or decrease in tumor markers.

2- Progression-free survival. Defined by time from day 1 cycle 1 to death from any cause or radiological progression by RECIST 1.1, whichever occurs first. Patients alive and without progression at the time of study analysis will be censored for time-to-event analysis.

3- Radiological response rate. Assessed by RECIST 1.1 criteria.

4- Rate of Biochemical response. Defined by at least 30 percent drop in the tumor marker (24-hour urine 5-hydroxyindoleacetic acid (5-HIAA) and/or specific hormone), if functioning syndrome, at any time of treatment in relation to pre-treatment value.

5- Quality of life. Assessed by the EORTC QLQ-C30 and QLQ-GINET21; both available in Brazilian Portuguese. Improvement of at least 10% in the baseline score at 3 and 6 months after the end of the treatment will be considered clinically meaningful. Improvement by 10% of the baseline score at 3 and 6 months will be considered clinically meaningful.

6- Incidence of Treatment-related Adverse Events. Frequency of adverse events of grades 2 or more by Common Adverse Event Toxicity Criteria (CTCAE) version 5.0.

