#### **Inclusion criteria**

- Age greater than or equal to 18 years.
- Well-differentiated metastatic NET from GEP, unknown primary with hepatic metastases or advanced/metastatic lung, inoperable, with no possibility of curative treatment.
- MIBG-I scintigraphy with positive expression in at least one lesion that presents significant uptake and compatible with therapeutic effectiveness.

- Disease with radiological progression (at least 10% tumor volume growth) in the last 12 months or with clinical and biochemical progression to functional NET according to clinical judgment.
- Progression or intolerance to previous standard treatments according to scenario (private [somatostatin analogue, everolimus] or public [somatostatin analogue]).
- Measurable disease.
- ECOG performance scale 0 to 2.
- Adequate organic function as defined by the following criteria:
  - Aspartate serum aminotransferase (AST), alanine serum aminotransferase (ALT)  $\leq$  2.5 times the upper limit of normal of the local laboratory (ULN-LL);
  - Total serum bilirubin  $\leq$  2.0 x ULN-LL;
  - Absolute neutrophil count  $\geq$  1,500/mm^3;
  - Platelet count  $\geq$  100,000/mm^3;
  - Hemoglobin  $\geq$  9.0 g/dL;
  - Estimated creatinine clearance using the MDRD equation  $\geq$  60ml/min
  - Informed consent form signed by the patient or legal representative.

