#### Quality of Life Assessment:

The quality-of-life assessment will be conducted by two questionnaires from the European Organization for Research and Treatment of Cancer Quality of Life Questionnaire group, composed of the general questionnaire EORTC QLQ-C30 and its specific domain for TNE, the QLQ-GINET21, both available in Portuguese of Brazil by cross-cultural validation.

The QLQ – C30 general quality of life questionnaire was developed for cancer patients and is one of the most used in clinical cancer research, having already been applied by more than 80,000 cancer patients. Version 3 is the one currently used. It is

multidimensional, can be self-administered and consists of 30 questions that assess the patient in the last two weeks. The questionnaire addresses general questions about cancer, such as symptoms, side effects of treatment, psychological suffering, physical functioning, social interaction, sexuality, body image, global health, quality of life and satisfaction with medical care, regardless of the type of cancer. It is a generic quality of life document for cancer, composed of 30 questions that define the general quality of life, through five functional scales (physical, role/performance, cognitive, emotional and social), three symptom scales (fatigue, pain and nausea/vomiting) and six simple items (dyspnea, insomnia, loss of appetite, constipation, diarrhea and financial difficulties).

The scale in this questionnaire constitutes the following score: 1 (no), 2 (little), 3 (moderately), and 4 (a lot), except the global health scale. This consists of 2 questions that ask the individual to rate their general health and quality of life in the last week, through a score from 1 to 7, 1 being terrible and 7 being excellent. Scores are calculated separately for each of the scales (functional, QOL and symptoms), ranging from zero - 100. On the Global Health and functionality scale, the higher the score, the better the quality of life. In the symptom scales, the higher the score, the worse the score. In order to know the calculation in each scale, the average score in each of the scales is performed. After this average we make the linear transformation for the score to be 0-100, according to the formulas below:

- Gross score or Raw Score (RS): adds the score of each item and divides it by the number of items

- S score for functional scales:  $\{1 - (RS - 1) / \text{variation}\} \times 100$

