- S score for symptom scale:  $\{(RS - 1) / \text{variation}\} \times 100$

- S-score for general health status / general quality of life:  $\{(RS - 1) / \text{variation}\} \times 100$

The variation is generally 3, since the items score from 1 to 4, except for the global health and quality scales that score a maximum of 7 and, therefore, there is a general variation of 6.

The complement of the QLQ-C30 for TNE, the QLQ-GINET21 questionnaire, is composed of 5 multi-item scales that address common symptoms in patients with NET, such as gastrointestinal and endocrine, concerns about illness, social role and symptoms of treatments; it also contains five items that assess weight loss/gain, bone/muscle pain,

sexual function. The methodology for calculating the scores is the same as that used by the questionnaire QLQ-C30.

Missing data often occurs in questionnaire studies. Researchers will try to minimize missing data by providing guidance to study participants. However, if it still occurs, several imputation methods can be used, and there is no standard method. The most common is to calculate the average of the scale of the answered items and use this average to input the missing value, provided that at least 50% of the items of that scale have been answered. This will be the method used in this study to treat possible missing data. When missing data occurs in single items, they should be excluded from the analysis.

The EORTC quality of life questionnaires will be applied at the baseline (within 4 days of treatment) and every 12 weeks (window of +/- 5 days) until the study leaves. The administration should preferably be on the day of the image, and always before the patient knows the result of the exam (so that the result does not influence the responses to the questionnaires) and by a trained investigator.

The total time to complete the QLG-C30 and LQL-GINET21 is approximately 20 to 30 minutes. The patient himself will complete the questionnaires; however, he may be helped by an investigator, if in doubt. In the end, it will be inserted in a closed envelope to ensure confidentiality and privacy.

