### **Statistical plan**

Descriptive statistics will be used to report population characteristics, binary outcomes and adverse events. The Kaplan-Meier method will be used to report time-to-event variables and the reverse Kaplan-Meier method will be used to calculate the follow-up time for patients. For the analysis of quality of life, we will report the proportion of patients who increase the sum of the total score by at least 10% at 3 and 6 months after treatment - improvement of at least 10% is considered to be clinically significant by patients. We will also evaluate whether the global score varies and how much varies during the study for each patient; this analysis will be carried out in percentage and descriptively. The scores will be calculated according to the instruction manual of the EORTC group. The quality-of-life analysis will be carried out using the

intention to treat method, where patients who do not respond will be considered “non-responders” in terms of the effectiveness of the treatment.

Missing data in the questionnaires will be dealt with as described in the section above "Quality of Life Assessment".

The study sample will be 22 patients. For this calculation, we considered the 40-month disease control rate H0 to be 40% (placebo arm of phase III studies in TNE, such as the RADIANT417 study), H1 to 67%. Two-tailed type I error margin of 10%, power of 80% and loss of follow-up / non-adherence of 10% were considered.

We estimated a 40% screening failure (40% positivity on MIBG-I131).

All analyzes will be by intention to treat. Patients who receive at least one dose of MIBGI131 will be evaluated for toxicity and efficacy.

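### For functional NET the primary endpoint demands a 10% relative improvement in GINET21, so a patient already at the best possible score cannot count as controlled, and no rule covers that case

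*Combined protocol and SAP*

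**What the plan says.** - **Objective.** Under Objectives – Primary, the second objective is "Control of clinical/biochemical (functional NET) at 6 months after the end of treatment".
- **Endpoint.** Under Outcomes – Primary, DCR is absence of RECIST 1.1 progression at 6 months after the end of treatment. For functioning syndrome it adds that "patients should have improved in at least 10% of the baseline score of quality-of-life (EORTC QLQ-GINET21) and stability or decrease in tumor markers". Outcomes – Secondary repeats this for the 3-month DCR and, for quality of life, states: "Improvement by 10% of the baseline score at 3 and 6 months will be considered clinically meaningful".
- **Entry.** The Inclusion criteria admit "Disease with radiological progression (at least 10% tumor volume growth) in the last 12 months or with clinical and biochemical progression" for functional NET. The two routes are alternatives, and neither requires a minimum GINET21 score.
- **Scoring.** Under Quality of Life Assessment, for the QLQ-C30: "Scores are calculated separately for each of the scales (functional, QOL and symptoms), ranging from zero - 100". A higher symptom score is worse. For GINET21: "The methodology for calculating the scores is the same as that used by the questionnaire QLQ-C30".
- **Analysis.** For quality of life, the Statistical plan reports the proportion of "patients who increase the sum of the total score by at least 10" percent. No GINET21 total is defined in the scoring section.

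No section gives a rule for a zero or low baseline, or a minimum absolute change.

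**The concern.** Three components decide success in a functional patient. For imaging and for markers, stability is enough. Only the symptom component requires improvement, and it measures that improvement against the patient's own starting score. Two problems follow.

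1. **At the floor.** A functional patient may enter on radiological progression with syndrome symptoms already controlled. If the relevant baseline score is 0, no improvement exists to be made. Followed as written, the rule records a failure whatever the tumour and markers do.
2. **Above the floor.** Ten percent of a small number is a very small number. At low non-zero baselines the required change can be less than one answer category on one item, so chance variation in one answer may pass as improvement.

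The result is then compared with a single 40% null in a single-arm study of 22 patients. The proportion functional, and their symptom level at entry, can move the observed DCR for reasons unrelated to the treatment.

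**Working it through.** **The plan's own figure.** Inputs from the Statistical plan: H0 40%, H1 67%, two-sided alpha 10%, power 80%, losses 10%.

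n = [(1.645 × √(0.40 × 0.60) + 0.842 × √(0.67 × 0.33)) / 0.27]² = 19.8, so 20. Then 20 × 1.1 = 22 (20/0.9 gives 23). The stated 22 is reproduced. The calculation uses one DCR for everybody, with no allowance for a stricter definition in functional patients.

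**Floor on a 0-100 symptom scale.** The score is S = (RS − 1)/3 × 100, where RS is the mean of items scored 1 to 4. If every item is answered 1, then RS = 1 and S = 0. No lower score exists, so no improvement is possible. Taken literally, 10% of 0 is 0 and an unchanged score might pass, but the text requires the patient to have improved.

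**Size of one answer step.** On a scale of k items, one category on one item moves S by 100/(3k) points. That is at least 10% of baseline when S ≤ 1000/(3k). Items per GINET21 scale are not in the documents, so k is shown as a range.

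| k | One step (points) | One step is enough from non-zero baselines up to |
|---|---|---|
| 1 | 33.3 | 100 (always) |
| 2 | 16.7 | 100 (always) |
| 3 | 11.1 | 100 (always) |
| 4 | 8.3 | 83.3 |
| 5 | 6.7 | 66.7 |
| 6 | 5.6 | 55.6 |

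**Other readings of the score.** These assume 21 items in total, inferred from the questionnaire's name.

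- *Average over 21 items, 0-100:* one step is 100/63 = 1.59 points. A baseline of 0 is blocked. From 1.6 to 15.9 one step is enough, from 17.5 to 31.7 two are needed, and at 100 seven.
- *Untransformed sum, 21 to 84:* sums of 21, 22 and 23 are blocked, because three steps are needed and only 0 to 2 are available. Three steps are needed at 24 to 30 and nine at 84. One step is never enough.
- *Total reversed so that higher is better:* scores of about 92 and above are blocked. One step is enough only at 15.9 or below.

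Some patients are blocked under every reading. The one-step problem appears only under some.

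**Possible effect on the DCR.** Let g be the share functional and h the share of these at the floor. Neither is in the documents. If floor status is independent of control, the maximum DCR is 0.67 × (1 − g × h). Exact power is for n = 22 with success declared at 14 or more responders (upper-tail alpha 0.021; 13 or more would give 0.055, above 5%).

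| g | h | Maximum DCR | Exact power |
|---|---|---|---|
| – | 0 | 0.670 | 0.72 |
| 0.5 | 0.1 | 0.67 × 0.95 = 0.6365 | 0.60 |
| 0.5 | 0.2 | 0.67 × 0.90 = 0.603 | 0.47 |
| 0.5 | 0.3 | 0.67 × 0.85 = 0.5695 | 0.34 |

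**The case against.** - **Requiring improvement may be deliberate.** The Hypotheses section expects improved quality of life, and the Statistical plan supports the 10% with a cited source. That stands as a reason to keep the requirement for patients who can improve. It does not justify failing those who cannot.
- **Functional patients have symptoms.** The Introduction describes functioning tumours as causing clinical symptoms, so a score of 0 may be rare. On a total over all items it would need the best answer throughout, including disease worries and social role. This limits the frequency, which the documents do not give. It is less persuasive if a single symptom scale is used and symptoms are already controlled at entry.
- **A reader might infer that anyone near the floor can never be controlled.** On 0-100 symptom scoring this is wrong: only exactly 0 is blocked, and patients just above it pass most easily. A blocked zone beyond the single best score appears only on an untransformed sum or a reversed total.
- **A reader might infer that one answer step is generally enough.** This depends on a scale and item count that the documents do not fix, and it fails on the untransformed sum.
- **An absolute 10-point rule would not cure coarseness.** On scales of 3 items or fewer, one step is already at least 11.1 points. This is correct and bears on the choice of scale.

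**Conclusion.** The concern holds in a limited form. As written, the rule counts a functional patient at the best possible baseline score as a primary failure despite no progression and stable or lower markers. This conflicts with an objective worded as control and with the treatment of non-functional patients. It is a stated rule giving a wrong result, and not only missing detail. The relative threshold also becomes trivially small at low non-zero baselines on 0-100 scoring. How often that matters cannot be said until the score is named, because the endpoint names no scale and the Statistical plan counts an increase where a higher symptom score is worse.

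The size is unknown. The ceiling of about 64% to 57% is an illustration resting on three assumptions: half the patients functional, 10% to 30% of these at the floor, and floor status independent of control. The documents support none of these figures, and the effect would be nil if no functional patient enters at the floor. The sample size of 22 is not contradicted by this point. The change should be made because the flaw sits in the primary endpoint and is cheap to remove.

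**What to change.** Before any outcome data are reviewed, amend Outcomes – Primary, Outcomes – Secondary and the Statistical plan so that they agree:

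1. Name one GINET21 scale, preferably with more than 3 items, and state which direction is improvement.
2. State the threshold in absolute points on 0-100. With 10 points, for example, a 4-item scale needs two answer steps (16.7 points), whereas a 3-item scale needs only one (11.1).
3. For functional patients whose baseline lies below that threshold, and who therefore have no room to improve, define clinical control as no worsening by that amount. Keep the improvement requirement for the others.
4. Report symptomatic improvement separately, among patients with room to improve.
5. Report radiological DCR alone for all patients, and state which definition is tested against the 40% null.

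The cost is a protocol amendment and a slightly more complex endpoint definition. No new data are needed, since GINET21 is already collected at baseline and every 12 weeks. Moving every functional patient from must improve to must not worsen is open to the sponsor, but it loosens the primary endpoint and would require the 40% null to be justified again.
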